8.1.1.3 Early Treatment Termination

Subjects who prematurely discontinue study drug treatment during the Treatment Period in Study 110 will be asked to complete the Early Treatment Termination Visit and the Safety Follow-up Visit. The Early Treatment Termination Visit assessments are listed in [Table 3-1](#).

The Early Treatment Termination Visit should be scheduled as soon as possible after the subject decides to terminate study treatment. If the Early Treatment Termination Visit occurs 3 weeks or later following the last dose of study drug, then the Safety Follow-up Visit will replace the Early Treatment Termination Visit (i.e., the assessments performed will be those specified for the Safety Follow-up Visit in [Table 3-1](#)), and an Early Treatment Termination Visit will not be required.

With the exception of [REDACTED] subjects who cannot access the commercial product after regulatory approval because reimbursement by the subject's insurance carrier (whether government or private payer) is not yet available or because the subject lacks insurance coverage, subjects who become eligible to receive commercially-available LUM/IVA by prescription of a physician may be discontinued from study drug dosing and will complete the Early Treatment Termination Visit (before commercially-available LUM/IVA dosing begins). The Safety Follow-up Visit will not be required if the subject immediately continues on commercially-available LUM/IVA.

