7.1 Overall Design

This is a Phase 3, multicenter study in subjects aged 6 years and older with CF who are homozygous for the *F508del-CFTR* mutation and who participated in Study 109 or Study 011B. Study 110 is designed to evaluate the safety and efficacy of long-term treatment of lumacaftor in combination with ivacaftor.

This study consists of Treatment Cohorts (Treatment Cohort Period 1 and Treatment Cohort Period 2) and an Observational Cohort. Treatment Cohort Period 1 and the Observational Cohort will be enrolled in parallel as shown in Figure 7-1.

Figure 7-1 Schematic of Study Design

IVA: ivacaftor; LUM: lumacaftor; q12h: every 12 hours.

- ^a The following subjects may be eligible for enrollment in the Treatment Cohort: (1) subjects who completed 24 weeks of study drug treatment (i.e., lumacaftor in combination with ivacaftor or placebo) in Study 109 or completed 24 weeks of study drug treatment and the Week 26 Safety Follow-up in Study 011B (NOTE: the last dose of study drug is the evening dose administered the day before the Week 24 Visit or the dose at the Week 24 Visit [based on the applicable protocol version for which a subject screens (provides consent/assent) under] in Study 109 or the evening dose administered the day before the Week 24 Visit in Study 011B) and (2) subjects who are not receiving study drug treatment at the end of the Treatment Period in Study 109 or Study 011B (NOTE: subjects from Study 011B have a planned Washout Period from Week 24 to Week 26 and must still complete the Week 26 Safety Follow-up), including subjects that require study drug interruption to be either continued or initiated at Day 1 in Study 110, and who have received Vertex approval for entry. Subjects who prematurely discontinued study drug treatment are not eligible for enrollment in the Treatment Cohort.
- ^b Subjects who turn 12 years of age in the previous study or Day 1 of this rollover study will begin receiving LUM 400 mg q12h/IVA 250 mg q12h on Day 1. Subjects who turn 12 years of age after the Day 1 Visit of this rollover study will begin receiving LUM 400 mg q12h/IVA 250 mg q12h at their next scheduled visit.
- ^c The Safety Follow-up Visit is scheduled to occur 4 weeks (\pm 7 days) after the last dose of study drug.
- ^d Subjects 6 through 11 years of age who complete Treatment Cohort Period 1 may enter Treatment Cohort Period 2. Week 96 of Treatment Cohort Period 1 will be the start of Treatment Cohort Period 2.

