10.3.2.2 Analysis of Secondary Endpoints

10.3.2.2.1 Analysis of Secondary Endpoints

The analysis of secondary efficacy endpoints will be conducted for the Treatment Cohort Period 1 only.

Absolute change from baseline in LCI_{2.5}

The analysis for efficacy endpoints will be focused on within-group comparison and summaries. No between-groups comparisons will be performed.

For Treatment Cohort Period 1, the mixed model repeated measures (MMRM) analysis will be used for the Cumulative Study Period based on the FAS. It will include two treatment groups (L200/I-L/I and P-L/I) using baseline of the Previous Study Period.

The absolute change from previous study baseline (including all measurements at each visit, both on-treatment measurements and measurements after treatment discontinuation), will be included as the dependent variable; treatment group, visit, and treatment-by-visit interaction, as fixed effects; and subject as a random effect with adjustment for previous studies (Study 109 versus Study 011B), weight (<25 kg versus \geq 25 kg), and ppFEV₁ severity (<90 versus \geq 90), both as determined at screening in the previous studies, and previous study baseline LCI_{2.5} as a continuous variable.

In the model, visit will be treated as a class variable, and an unstructured covariance matrix will be assumed to model the within-subject variability. This model imposes no assumptions on the correlational structure and is considered robust. If there is a convergence problem due to the unstructured covariance matrix, the unstructured covariance matrix will be replaced by compound symmetry in the primary analysis. Denominator degrees of freedom for the *F*-test for fixed effects will be estimated using the Kenward-Roger approximation.¹ With a mixed-effects model as the primary analysis model based on restricted maximum likelihood estimation and assuming that conditional on fixed and random effects data are missing at random, no imputation of missing data will be done.

The result obtained from the model will be the treatment effect at each post baseline visit. The estimated mean within-group treatment effect, i.e., Least Square (LS) Means, SE, 95% CI, and a 2-sided within treatment group *P* value, will be provided. The LS means of absolute change from previous study baseline with 95% CI at each visit during the Cumulative Study Period will be plotted by treatment groups (L200/I-L/I and P-L/I).

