13 APPENDICES

Appendix A Schedule of Assessments

Schedules of Assessments are shown in Table 13-1 (Treatment Cohort Period 1), Table 13-2, (optional Treatment Cohort Period 2), and Table 13-3 (Observational Cohort). All visits are to be scheduled relative to the Day 1 Visit (first dose of study drug). For example, the Week 8 (± 1 week) Visit would occur after 8 weeks of study drug administration has been completed (i.e., Day 57, first day of Week 9).

Table 13-1 Study VX15-809-110: Treatment Cohort Period 1

Event/Assessment ^a	Treatment Period							Early Treatment Termination Visit ^{d,e}	Safety Follow-up Visit (4 weeks [± 7 days] After Last Dose) ^{d,e}
	Day 1 ^b	Day 3 (± 1 day)	Day 15 (± 3 days) and Week 4 (± 1 week)	Week 8, Week 16, Week 24, Week 36, Week 48 (± 1 week)	Week 12, Week 20 (± 1 week)	Week 60, Week 84 (± 1 week)	Week 72 (± 1 week)		
Clinic visit	X		X	X	X ^{f,g}	X	X	X	X
Telephone contact ^h		X			X ^{g,i}				

^a All assessments will be performed before study drug dosing unless noted otherwise (Protocol Section 11.1).

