^d Subjects who prematurely discontinue study drug treatment during the Treatment Cohort Period 1 in Study 110 will be asked to complete the Early Treatment Termination Visit and the Safety Follow-up Visit (Protocol Section 8.1.1.3). The Early Treatment Termination Visit should be scheduled as soon as possible after the subject decides to terminate study treatment. If the Early Treatment Termination Visit occurs 3 weeks or later following the last dose of study drug, then the Safety Follow-up Visit will replace the Early Treatment Termination Visit (i.e., the assessments performed will be those specified for the Safety Follow-up Visit in Table 13-1), and an Early Treatment Termination Visit will not be required. Subjects who enter Treatment Cohort Period 2 do not need to complete the Safety Follow-up Visit.

^e With the exception of [REDACTED] subjects who cannot access the commercial product after regulatory approval because reimbursement by the subject's insurance carrier (whether government or private payer) is not yet available or because the subject lacks insurance coverage, subjects who become eligible to receive commercially-available LUM/IVA by prescription of a physician may be discontinued from study drug dosing and will complete the Early Treatment Termination Visit (before commercially-available LUM/IVA dosing begins). The Safety Follow-up Visit will not be required if the subject immediately continues on commercially-available LUM/IVA.

^f LFTs (ALT, AST, GGT, ALP, and total bilirubin) will be performed at these visits. Although blood samples are to be collected and analyzed at a central laboratory, a local laboratory may be used if a subject cannot return to the clinical study site for the blood draw (Protocol Section 11.7.3).

^g A urine pregnancy test will be performed for all female subjects of childbearing potential before the Week 12 and Week 20 telephone contacts, and the results made available before the contact. The urine pregnancy test may be performed at home or at the site.

^h Telephone contacts will be made to assess the subject's status, any AEs, concomitant medications, treatments, and procedures.

Statistical Analysis Plan (Methods)
 Vertex Study: VX15-809-110 Protocol V2.0 Dated 15 September 2015

Table 13-1 Study VX15-809-110: Treatment Cohort Period 1

Event/Assessment ^a	Treatment Period								Early Termination Visit ^{d,e}	Safety Follow-up Visit (4 weeks [\pm 7 days] After Last Dose) ^{d,e}

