Appendix D Analysis Visit Window Mapping Rules for Efficacy and Safety Measurements

Table 13-5 Visit Window Mapping Rules for Study 110 Visits

Assessments	Study 110 Visit	Target Study Day	Visit Window (in Study Days)	
• Spirometry (see special handling below)	110 Day 15	15	(1, 22]	
	110 Week 4	29	[23, 43]	
	• Weight and height	110 Week 8	57	[44, 85]
		110 Week 16	113	[86, 141]
	• Vital Signs	110 Week 24	169	[142, 211]
		110 Week 36	253	[212, 295]
		110 Week 48	337	[296, 379]
		110 Week 60	421	[380, 463]
		110 Week 72	505	[464, 547]
		110 Week 84	589	[548, 631]
110 Week 96		673	[632, 687]	
110 Follow-up	701	Nominal Visit		
• Labs	110 Day 15	15	(1, 22]	
	○ Chemistry (Except LFT)	29	[23, 43]	
	○ Hematology	57	[44, 85]	
	110 Week 16	113	[86, 141]	
	110 Week 24	169	[142, 211]	
	110 Week 36	253	[212, 295]	
	110 Week 48	337	[296, 421]	
	110 Week 72	505	[422, 589]	
	110 Week 96	673	[590, 687]	
	110 Follow-up	701	Nominal Visit	
• Chemistry (LFT)	110 Day 15	15	(1, 22]	
	110 Week 4	29	[23, 43]	
	110 Week 8	57	[44, 71]	
	110 Week 12	85	[72, 99]	
	110 Week 16	113	[100, 127]	
	110 Week 20	141	[128, 155]	
	110 Week 24	169	[156, 211]	
	110 Week 36	253	[212, 295]	
	110 Week 48	337	[296, 379]	
	110 Week 60	421	[380, 463]	
	110 Week 72	505	[464, 547]	
	110 Week 84	589	[548, 631]	
	110 Week 96	673	[632, 687]	
110 Follow-up	701	Nominal Visit		
• Coagulation	110 Day 15	15	(1, 22]	
• CFQR, TSQM	110 Week 4	29	[23, 71]	
	110 Week 16	113	[72, 141]	

• TSQM	110 Week 24	169	[142, 253]
	110 Week 48	337	[254, 505]
	110 Week 96	673	[506, 687]
	110 Follow-up	701	Nominal Visit
• Urinalysis (including urine microscopy)	110 Week 16	113	(1, 141]
	110 Week 24	169	[142, 253]
	110 Week 48	337	[254, 505]
	110 Week 96	673	[506, 687]
	110 Follow-up	701	Nominal Visit
• Ophthalmologic examination	110 Week 48	337	[254, 505]
	110 Week 96	673	[506, 687]
	110 Follow-up	701	Nominal Visit
• Standard ECG	110 Day 15	15	(1, 22]
	110 Week 4	29	[23, 43]
	110 Week 8	57	[44, 85]
	110 Week 16	113	[86, 141]
	110 Week 24	169	[142, 253]
	110 Week 48	337	[254, 421]
	110 Week 72	505	[422, 589]
	110 Week 96	673	[590, 687]
	110 Follow-up	701	Nominal Visit
• Sweat Chloride	110 Day 15	15	(1, 22]
	110 Week 4	29	[23, 99]
	110 Week 24	169	[100, 421]
	110 Week 96	673	[422, 687]
• LCI	110 Day 15	15	(1, 22]
	110 Week 4	29	[23, 99]
	110 Week 24	169	[100, 253]
	110 Week 48	337	[254, 505]
	110 Week 96	673	[506, 687]

Special handling for spirometry assessments:

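### Table 13-5 puts every Safety Follow-up record in one visit level, and the MMRM as written pools early stoppers with Week 96 completers there, which matters for growth measures

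*SAP*

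**What the plan says.** SAP Appendix D, Table 13-5, places almost all Study 110 records by actual study day. The exceptions are the Day 1 and Day 15 serial spirometry and the Follow-up row, which reads "110 Follow-up 701 Nominal Visit". That row appears for spirometry, height and weight, vital signs, laboratory tests, CFQ-R, TSQM, ophthalmology and ECG. It does not appear for LCI or sweat chloride.

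The Safety Follow-up Visit is defined relative to the last dose: 4 weeks later, give or take 7 days (Protocol 8.1.1.2; SAP 7.1). Children who stop early "will be asked to complete the Early Treatment Termination Visit and the Safety Follow-up Visit" (SAP Appendix A, Table 13-1 footnotes).

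SAP 10.3.2.2.1 models change from the parent-study baseline, "including all measurements at each visit, both on-treatment measurements and measurements after treatment discontinuation". Visit is a class variable with an unstructured covariance matrix, and LS means are reported and plotted at each visit of the Cumulative Study Period. SAP 9.1.3 ends that period on the last day in Study 110, so Follow-up lies inside it. SAP 10.3.2.2.1 and 10.3.2.2.2 apply the same model to BMI, weight, height, their z-scores, ppFEV1, CFQ-R and TSQM.

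**The concern.** A class-variable visit factor assumes that each level is one occasion. The Follow-up level is one occasion in time off drug but not in time since baseline. In growing children, the change from baseline in height, weight or BMI depends mainly on time since baseline.

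Two results are at stake. The first is the Follow-up LS mean with its CI and nominal P value, which would mix very different lengths of follow-up. The second is the Week 96 LS mean. Under an unstructured covariance, completers teach the model that Follow-up lies close to Week 96. An early stopper's low Follow-up value then makes that child's missing Week 96 value look low too. Long-term efficacy and durability are a secondary objective, so late-visit estimates are the ones readers will look at.

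**Working it through.** **1. The plan's own figure.** The schedule in SAP Appendix A puts the Week 8 visit at "Day 57, first day of Week 9", so Week w is Day 7w + 1.
- Week 96: 7 × 96 + 1 = 673.
- Follow-up: 673 + 28 = 701, which reproduces Table 13-5. With ±7 days the range is 694 to 708.

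**2. Follow-up day for early stoppers** (last dose at Week w, Day 7w + 1 + 28).

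| Last dose | Follow-up day |
|---|---|
| Week 8 | 85 (78 to 92) |
| Week 24 | 197 |
| Week 48 | 365 |
| Week 72 | 533 |
| Week 96 | 701 |

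The Week 8 stopper is seen 701 − 85 = 616 days, or 88 weeks, before the listed target but carries the same label.

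**3. Time since parent-study baseline.** For a Study 109 child with no roll-over gap this is 24 + w + 4 weeks:
- stop at Week 2: 30 weeks
- stop at Week 8: 36 weeks
- complete Week 96: 124 weeks

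Study 011B children add the 2-week washout.

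**4. Size at the Follow-up level, by hand.** Assume growth of 5.5 cm/year (not in the documents) and 52.18 weeks per year.
- Week 8 stopper: 5.5 × 36 / 52.18 = 3.8 cm.
- Completer at Follow-up: 5.5 × 124 / 52.18 = 13.1 cm.
- At Week 96 itself: 5.5 × 120 / 52.18 = 12.6 cm.

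If stopping is uniform over Weeks 2 to 90, the mean stop is Week 46. That is 50 weeks short of Week 96, or 5.5 × 50 / 52.18 = 5.3 cm. The raw Follow-up mean is low by this gap times the early stoppers' share of Follow-up records (all early stoppers assumed to attend):
- 10% stop, all completers attend: share 0.10 / (0.10 + 0.90) = 10%, error about 0.5 cm.
- 20% stop, 20% of completers attend: share 0.20 / (0.20 + 0.80 × 0.20) = 56%, error about 2.9 cm.

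**5. Size at Week 96, by simulation.** The shift through the covariance matrix has no simple closed form. The simulations fitted one group by maximum likelihood with an unstructured covariance, with and without a Follow-up level. Typical inputs were 240 children, growth SD 0.9 cm/year, 10 to 20% stopping over Weeks 2 to 90, and 20 to 100% of completers attending Follow-up. All of these are assumptions.
- With the level in the model, the Follow-up mean height change was 0.6 to 2.1 cm low and Week 96 was 0.1 to 0.6 cm low.
- Without it, Week 96 was within 0.06 cm of the truth.
- Runs with other residual SDs gave Week 96 errors of about 0.05 to 0.46 cm.
- The two large errors arise in different settings. At 20% attendance and 20% stopping, Follow-up was about 2.6 cm low and Week 96 only about 0.05 cm low. At full attendance, Week 96 was 0.27 to 0.46 cm low and Follow-up 0.5 to 1.0 cm low.

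**6. ppFEV1.** With an assumed decline of 1.5 points/year, the Follow-up mean was about 0.1 to 0.75 points too high. Week 96 moved by 0.1 points or less, at or below the one decimal in SAP Appendix B.

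Weight and BMI were not simulated. The mechanism is the same, but no size is claimed for them.

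**The case against.** **The SAP never says that Follow-up is an MMRM level.** This is true. The shell in Table 10-2 ends in an ellipsis, and the protocol's Cumulative Dosing Period (12.3) ends at the last dose, which would leave Follow-up out. But the SAP moves the end to the last day in Study 110 and asks for all measurements at each visit, including after discontinuation. A programmer following that text would include it.

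**The nominal rule has a purpose.** Follow-up means 4 weeks after last dose for every child, and the rule keeps off-drug values out of treatment-visit rows. That is a fair reason to keep the label for descriptive tables. It is not applied throughout: Table 13-5 has no Early Treatment Termination row, so those off-drug values go to day windows. An off-drug value at 20 days is windowed, while one at 21 days becomes a Follow-up value, because from 3 weeks the Follow-up Visit replaces the termination visit.

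**A reader might infer that an early stopper's value is analysed as if taken on Day 701.** The documents do not support this. The only stated use of a target day is to choose among several records in one window (SAP 10.1). The MMRM has no numeric day, and the rate-of-change model uses treatment duration. The fault is pooling within a level.

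**A reader might also infer that early stoppers are over-represented because of the commercial-drug exemption** ("The Safety Follow-up Visit will not be required if the subject immediately continues on commercially-available LUM/IVA"). That exemption is written for children who discontinue study drug, so it removes early stoppers from Follow-up. The Period 2 exemption does remove completers, but only French children aged 6 through 11. Nothing in the documents points to 20% attendance among completers.

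**The stakes are limited.** P values are nominal and no between-group comparison is planned. Height is an other secondary endpoint, and the z-scores already adjust for age. All of this stands, and it limits how much the point matters.

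**Conclusion.** The point holds as a fault in the model specification with limited reach. As written, one MMRM level mixes changes over about 30 to 124 weeks. For height, weight and BMI the Follow-up mean change then has no clear meaning, and the Week 96 LS mean can be pulled down. For height the pull is roughly 0.1 to 0.6 cm of about 12.6 cm, against 0.06 cm or less when the level is left out. These sizes rest on assumed growth, dropout, attendance and residual variation, and on a one-group simplification of the planned model.

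It would be wrong to conclude that the Week 96 durability estimates are compromised in general. LCI2.5, LCI5.0 and sweat chloride have no Follow-up row, the Week 96 effect on ppFEV1 is negligible, and event and threshold safety summaries use the treatment-emergent period and not this mapping. It would also be wrong to quote the largest Follow-up error and the largest Week 96 error together.

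**What to change.** - In SAP 10.3.2.2.1, exclude the 110 Follow-up level from the MMRM visit factor and from the LS-mean plots. This step alone removes the Week 96 shift.
- In Table 13-5, state that Follow-up is relative to last dose and that target Day 701 applies to Week 96 completers only.
- Summarise Follow-up descriptively, with separate rows for completers and early stoppers.
- Optional: for the efficacy models, map early stoppers' Follow-up values by actual study day. A Week 8 stopper's spirometry or height would then fall in the Week 8 window (Days 78 to 85) or the Week 16 window (Days 86 to 92). This puts off-drug values in scheduled treatment-visit rows, and a record from the scheduled visit in the same window would take precedence.

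The cost is SAP wording and a small programming change, with no new data. Without the optional step, early stoppers' off-drug Follow-up values leave the MMRM. The sentence on including measurements after discontinuation should then say so.

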8.2.3 Rationale for Study Assessments

The safety assessments are standard parameters for clinical studies in drug development and are generally recognized as reliable, accurate, and relevant to the study of subjects with CF. Ophthalmologic examinations were added to the standard safety assessments.

Ophthalmologic Examinations: A juvenile rat toxicity study performed to support dosing of ivacaftor in subjects <2 years of age demonstrated lens opacities in some animals.²¹ Prior studies in rats and dogs of older age did not demonstrate similar findings. Given substantial differences between human and rat lens development, the finding is of unlikely relevance to humans. Periodic ophthalmologic examinations for children aged 11 years and younger receiving ivacaftor are being performed to confirm this interpretation. The overall data acquired to date does not suggest an association between ivacaftor treatment and cataract development; however, a potential association has not been fully excluded.

LCI Assessment (Subjects From Study 109 and the Study 011B LCI Substudy Only): LCI is a measure of ventilation inhomogeneity that is based on tidal breathing techniques which have been evaluated in patients as young as infants.^{31,32} Studies have shown that LCI correlates with FEV₁ in its ability to measure airway disease in patients with impacted spirometry assessment but can also detect lung disease at an earlier stage than spirometry.^{28,33} Furthermore, data from Study VX10-770-106 in CF patients with an FEV₁ >90% showed LCI to be a more sensitive outcome measure than FEV₁.

Spirometry: Because lung disease is the major cause of morbidity and mortality for patients with CF, CF lung disease is the desired primary target of lumacaftor therapy. FEV₁, as measured by spirometry, is the most widely implemented standardized assessment to evaluate lung function in CF and is therefore included as an assessment.

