The baseline of LCI will be the most recent visit with non-missing value before the initial administration of study drug in the corresponding Study Period.

- For ECG, the baseline will be defined as the average of the 3 pretreatment measurements on the start of each Study Period.
- For sweat chloride, the values at each visit will be based on the averaged measurements from left and right arms.
 - The current study baseline will be the value at the most recent visit before the first dose of Study 110.
 - The previous study baseline and cumulative study baseline will be the baseline from the previous study, i.e., average of the values at screening and the pretreatment measurement on Day 1 from the previous studies. If only 1 sweat chloride measurement before the first dose is available, that measurement will be considered the baseline.

Absolute Change from baseline: will be calculated as Post baseline value - Baseline value.

Relative change from baseline: will be calculated and expressed in percentages as $100 \times (\text{Post baseline value} - \text{Baseline value}) / \text{Baseline value}$.

Unscheduled Visits: Unscheduled visit measurements will be included in listings, for derivation of visit windows and computation of baseline/last on-treatment visit, and for the analysis of maximum/minimum values and maximum/minimum changes from baseline values.

Visit Windows: Table 13-5 defines the visit window mapping rules to derive the actual visits for the scheduled post-baseline measurements.

Repeated observations within the same visit window

- For all efficacy parameters, if there are multiple measurements within a visit window, the record at the scheduled visit will be used. If there are no measurements at the scheduled visit, then 1) the record closest to the target day will be used; or 2) if there are multiple records with the same distance to the target day, the latest record will be used.
- For all safety parameters, if there are multiple measurements within a visit window, then 1) the record closest to the target day will be used; or 2) if there are multiple records with the same distance to the target day, the latest record will be used.

BMI, weight, and height will follow safety and efficacy windowing rules. For predose spirometry, efficacy windowing rules will be applied. For postdose serial spirometry, analyses will be based on nominal assessment.

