10.4.6 Ophthalmological Examinations

Treatment Cohort Period 1

For the analysis of slit lamp lens, the number and percentage of subjects with shift changes from previous study baseline (normal versus abnormal) will be tabulated for the Previous Study Period based on the Safety Set, Current Study Period based on 110 Safety Set, and Cumulative Study Period based on the Safety Set at each scheduled time point following the safety presentation format in Section 10.1.2. Ophthalmological examination findings will also be presented as a data listing.

Treatment Cohort Period 2

Ophthalmological examination findings in Treatment Cohort Period 2 will be presented as a data listing.

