Standard 12-lead ECG ^t	X ^u	X		Weeks 8, 16, 24, 48				X	X		X	X
Serum β -hCG ^{j,k}	X											
Serum chemistry ^{k,v}	X	X		X	X ^{t,w} LFTs only	X ^{t,w} LFTs only		X	X		X	X
Hematology ^k	X	X		X	X ^{t,w} LFTs only	X ^{t,w} LFTs only		X	X		X	X
Coagulation studies ^{s,k}	X	X	X	Weeks 16, 24, 48				X	X		X	X
Urinalysis ^k	X			Weeks 16, 24, 48				X	X		X	X

^p An ophthalmologic examination will be conducted by a licensed ophthalmologist or optometrist (Protocol Section 11.7.6). Subjects with documentation of bilateral lens removal do not need the ophthalmologic examination. If a cataract or lens opacity is identified and determined to be clinically significant by a licensed ophthalmologist or optometrist at the Day 1 examination (also see Footnote b), the subject will be notified. After discussion with the site principal investigator and in collaboration with the Vertex medical monitor, the subject may elect to participate or not to participate in the study. If the subject continues in the study, more frequent ophthalmologic monitoring should be considered. If a cataract or lens opacity is identified and determined to be clinically significant by a licensed ophthalmologist or optometrist after dosing, the subject will be notified. After discussion with the site principal investigator, and in collaboration with the Vertex medical monitor, the subject may elect to continue or discontinue the study. If the subject discontinues study drug, they should complete the Early Treatment Termination Visit and Safety Follow-up Visit (see Protocol Section 8.1.1.3 for Early Treatment Termination). If the subject continues, more frequent ophthalmologic monitoring should be considered.

^q Subjects may complete the ophthalmologic examination within \pm 1 week of the scheduled visit.

^r An ophthalmologic examination will be conducted by a licensed ophthalmologist or optometrist at the Week 96 Visit (or the Early Treatment Termination Visit if the subject does not have a Week 96 Visit) OR the Safety Follow-up Visit (Protocol Section 11.7.6). Subjects with documentation of bilateral lens removal do not need the ophthalmologic examination.

^s Symptom-directed physical examinations will occur at any time during the study if triggered by AEs or if deemed necessary by the investigator (Protocol Section 11.7.4).

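### Lens examinations dated Study 110 Days 2 to 253 fit no analysis visit in SAP Table 13-5, so early-termination and additional examinations in that span are left out of the slit-lamp shift table

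*SAP*

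**What the plan says.** - SAP 10.1 on visit windows: "Table 13-5 defines the visit window mapping rules to derive the actual visits for the scheduled post-baseline measurements".
- SAP Appendix D, Table 13-5, for the lens examination: "Ophthalmologic examination 110 Week 48 337 [254, 505" (target Day 337, Days 254 to 505). The other entries are Week 96 (Days 506 to 687) and Follow-up, assigned by nominal visit. There is no ETT row.
- The same table for urinalysis, which also has no visit soon after Day 1: "110 Week 16 113 (1, 141". Its first window opens just after Day 1.
- SAP Appendix A, Table 13-1, schedules lens examinations at Day 1 and Week 48, with a closing examination at Week 96 "or the Early Treatment Termination Visit if the subject does not have a Week 96 Visit) OR the Safety Follow-up Visit". Protocol 11.7.6 also allows additional examinations at the investigator's discretion.
- SAP Appendix A, on children leaving for the marketed product: "The Safety Follow-up Visit will not be required if the subject immediately continues on commercially-available LUM/IVA". They do complete an ETT Visit.
- SAP 10.4.6 tabulates slit-lamp shifts from the previous-study baseline for the Previous and Current Study Periods and for the "Cumulative Study Period based on the Safety Set at each scheduled time point following the safety presentation format in Section 10.1.2". It also provides a data listing of findings.

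**The concern.** Ophthalmologic examinations are part of the primary safety endpoint. Protocol 8.2.3 says they were added because of lens opacities in juvenile rats. It judges the finding unlikely to be relevant to humans and sees no association in the data so far, but adds that "a potential association has not been fully excluded". The shift table is the planned summary of that question.

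The plan collects lens examinations during the first 36 weeks or so from children who stop early or are examined outside the schedule, yet the window rule gives those results nowhere to go in that summary. When few or no shifts are expected, a table that silently omits some post-dose examinations is hard to read: its denominators and counts both leave out part of the collected data.

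**Working it through.** **1. Reproduce the window limits.** Target days in Table 13-5 are Week 24 = 169, Week 48 = 337, Week 96 = 673 and Follow-up = 701. Taking midpoints of adjacent targets:

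- (169 + 337) / 2 = 253, so Week 48 opens on Day 254.
- (337 + 673) / 2 = 505, so Week 48 closes on Day 505.
- (673 + 701) / 2 = 687, so Week 96 closes on Day 687.

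All three match the table, so the limits are not a text-extraction fault. The lower limit is the Week 24/Week 48 midpoint, although no lens examination is scheduled at Week 24.

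**2. Size of the gap.** Days 2 to 253 are 253 − 2 + 1 = 252 days. Against the Week 96 target day, 252 / 673 = 37.4%. Against all post-Day-1 days up to the end of the last window, 252 / 686 = 36.7%.

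**3. Compare with the rest of the table.** Spirometry, weight and height, vital signs, chemistry, hematology, LFTs, coagulation, questionnaires, urinalysis, ECG, sweat chloride and LCI all have a first window opening just after Day 1. The lens examination is the only exception.

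**4. Which examinations are affected.**

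| Examination | Result under Table 13-5 |
|---|---|
| Week 48 on schedule (Day 337 ± 1 week) | Mapped to Week 48 |
| ETT or additional, Day 254 or later, up to Day 687 | Mapped to Week 48 or Week 96 |
| Closing examination at Safety Follow-up, any day | Mapped to nominal Follow-up |
| ETT or additional, Days 2 to 253 | No analysis visit |

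The examination date decides, not the stop date. An ETT Visit 3 weeks or more after the last dose is replaced by Safety Follow-up, so an ETT Visit falls at most 20 days after the last dose. Since 254 − 20 = 234, a child whose last dose is on Days 234 to 253 may still have an ETT examination that maps to Week 48. Using the extra week that Table 13-1 allows for the eye examination, the limit is 254 − 20 − 7 = 227.

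**5. Look for another rule that recovers them.**

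- SAP 10.1 uses unscheduled measurements in deriving visit windows, but that does not help where no window exists.
- SAP 10.1 also admits unscheduled measurements to maximum, minimum and last on-treatment summaries, but 10.4.6 plans none for the lens.
- Other safety shift tables are not limited to visits. LFT shifts (10.4.2) and ECG shifts (10.4.3) use the worst on-treatment evaluation. Pulse oximetry (10.4.5) uses the lowest value in the treatment-emergent period.
- SAP 9.1.3 applies the same selected records to the different periods under different labels, so a record not selected is missing from both the Current and the Cumulative tables.

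**The case against.** The strongest reply is that this is a narrow gap in one descriptive table. Much of that stands.

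- **A reader might infer that every child who stops before Day 254 leaves the table.** The documents do not support this. The closing examination may be done at Safety Follow-up, which is mapped by nominal visit, and some ETT examinations after a late stop fall on or after Day 254.
- **A reader might infer that these children lose their only post-baseline lens result.** They do not. There is a Study 110 Day 1 examination, or a recent one accepted in its place. Because shifts are from the previous-study baseline, that examination is already post-baseline for children previously on active drug. What is lost is the closing Study 110 examination.
- **A reader might infer that a true signal would vanish.** It stays in the listing. Protocol 13.1.1.2 also has clinically significant worsening on study assessments recorded as an AE. It does not name eye examinations, but its list is not exhaustive. Such a case could then appear in the TEAE tables and, if the child stopped because of it, among TEAEs leading to discontinuation and in the narrative listings. A child who stops for an opacity is also asked to attend Safety Follow-up, although a second lens examination there is not compulsory. The group with no Safety Follow-up leaves for reasons of drug access, so the documents do not show that the loss is driven by lens findings.
- **A programmer might treat ETT as a scheduled time point of its own.** The SAP does not say so. Table 13-5 names a nominal Follow-up row but no ETT row.

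None of this supplies a cell for an ETT or additional examination on Days 2 to 253. A listing or a possible AE record is not the planned summary of a primary safety component.

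**Conclusion.** The point holds in limited form. As written, the SAP leaves ETT and additional lens examinations dated Days 2 to 253 (252 days, about 37% of the time to Week 96) out of the slit-lamp shift table. The clearest case is a child who moves directly to commercial drug before Day 254: the ETT examination closes Study 110 for that child and is not tabulated.

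The number of children cannot be computed. It is tempting to apply an assumed early-stop rate, for example 5% to 15% of 256, which gives 0.05 × 256 = 12.8 and 0.15 × 256 = 38.4, or about 13 to 38. The documents give no such rate, 256 is the number potentially eligible rather than enrolled, and some of those children would be tabulated through Safety Follow-up. The documents also do not show whether anyone moved to commercial drug before Day 254. Those counts should not be used as an estimate.

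The conclusion rests on reading Table 13-5 and 10.4.6 literally and on the absence of another mapping rule in the SAP text available.

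**What to change.** In SAP 10.4.6, add a row for each child's worst post-baseline slit-lamp result in each Study Period, through the Safety Follow-up Visit and including ETT and unscheduled examinations. Keep the previous-study baseline as the reference. State the end point as the Safety Follow-up Visit rather than 28 days after the last dose, because that visit may fall up to 28 + 7 = 35 days after it. This follows the worst-value shifts already planned for LFTs, ECG and pulse oximetry.

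Optionally, also give ETT examinations before Day 254 their own row in Table 13-5, or open the first lens window at (1, 505]. The wider window is not enough alone. SAP 10.1 keeps the safety record closest to the target day, so a normal Week 48 result would displace an earlier abnormal one. Its downside is that the row then mixes examination times.

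The cost is a sentence of SAP text and one extra table row per Study Period, with no new data and no change to any study procedure.
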